6.7. Treatment Compliance

Subjects will be instructed to return their empty and unused study medication bottle at the Week 4 Visit or the Final Safety Visit, whichever occurs first. Site personnel will review returned and unused study medication to determine compliance.

Non-compliance will be otherwise defined as taking less than 80% or more than 120% of study medication as determined by capsule counts. If a study subject is non-compliant with study medication, the Site Investigator and staff should re-educate and train the subject in administration of study drug. Data indicating non-compliance will be used in the end of study analysis.

6.8. Study Drug Storage

The Site Investigator must ensure that all investigational drug supplies are kept in a locked, safe area at room temperature (68-77°F) with access limited to those directly involved in the study. Investigational drug supplies should not be repackaged in any way.

6.9. Warnings/Precautions

Mexiletine should be used cautiously in patients with known hypersensitivity to other class IB anti-arrhythmics. For this reason, subjects who have had a previous reaction to lidocaine will be excluded from this study. Mexiletine can uncommonly cause seizures, especially in patients with a known history of seizures and should be used cautiously in this setting. Cigarette smoking can diminish the efficacy of mexiletine and should be restricted in patients taking mexiletine. Mexiletine can also prolong the stimulant effects of caffeine and its intake should also be limited.

6.9.1. Death or Heart Attack

Antiarrhythmic drugs, similar to mexiletine, have been reported to increase the risk of death or heart attack, especially in people who have had a heart attack within the past 2 years. Mexiletine may increase the chance of having arrhythmias (irregular heartbeats) and has not been proven to help people without life-threatening arrhythmias to live longer.

6.9.2. Acute Liver Injury

In post-marketing experience abnormal liver function tests have been reported, some in the first few weeks of therapy with mexiletine. Most of these have been observed in the setting of congestive heart failure or ischemia and their relationship to mexiletine has not been established.

6.9.3. General

If a ventricular pacemaker is operative, patients with second or third degree heart block may be treated with mexiletine if continuously monitored. A limited number of patients (45 of 475 in controlled clinical trials) with pre-existing first degree AV block were treated with mexiletine; none of these patients developed second or third degree AV block. Caution should be exercised when it is used in such patients or in patients with pre-existing sinus node dysfunction or intraventricular conduction abnormalities.

Like other antiarrhythmics, mexiletine can cause worsening of arrhythmias. This has been uncommon in patients with less serious arrhythmias (frequent premature beats or non-sustained ventricular tachycardia), but is of greater concern in patients with life-threatening arrhythmias such as sustained ventricular tachycardia. In patients with such arrhythmias subjected to programmed electrical stimulation or to exercise provocation, 10-15% of patients had exacerbation of the arrhythmia, a rate not greater than that of other agents.

Mexiletine should be used with caution in patients with hypotension and severe congestive heart failure (CHF) because of the potential for aggravating these conditions.

Since mexiletine is metabolized in the liver, and hepatic impairment has been reported to prolong the elimination half-life of mexiletine, patients with liver disease should be followed carefully while receiving mexiletine. The same caution should be observed in patients with hepatic dysfunction secondary to congestive heart failure.

Concurrent drug therapy or dietary regimens which may markedly alter urinary pH should be avoided during mexiletine therapy. The minor fluctuations in urinary pH associated with normal diet do not affect the excretion of mexiletine.

6.9.4. Pregnancy & Nursing Mothers

Subjects or partners of male subjects should not become pregnant during the study. If a female subject becomes pregnant, study treatment must be discontinued immediately.

Reproduction studies performed with mexiletine hydrochloride in rats, mice and rabbits at doses up to four times the maximum human oral dose (24 mg/kg in a 50 kg patient) revealed no evidence of teratogenicity or impaired fertility but did show an increase in fetal resorption.

Mexiletine appears in human milk in concentrations similar to those observed in plasma. Therefore, no subject should nurse their infant while participating in this study.

6.9.5. Diaphragm Pacing System (DPS) Device

Subjects should not undergo DPS implantation surgery during the study. If a subject does undergo DPS implantation surgery during the study, study treatment must be discontinued immediately.

7.0. SAFETY VARIABLES AND OUTCOME MEASURES

7.1. Safety Variables

The safety of mexiletine will be evaluated using vital signs, weight, clinical laboratory determinations, physical examinations, AEs (including deaths and other SAEs), use of concomitant medications and treatment discontinuations (tolerability).

7.1.1. Vital Signs, Height and Weight

Vital signs will be obtained after the subject has been in a seated position for at least 3 minutes. Systolic and diastolic blood pressure, and pulse rate (radial artery) will be obtained at specified visits. Height will be measured and recorded at the Screening Visit only. Weight and vital signs will be measured and recorded at Screening, Pre-Dose and Post-Dose Baseline, Week 4, and Week 8 or the Final Safety Visit, if applicable.

7.1.2. Clinical Laboratory Assessments

The following laboratory tests will be performed to assess the safety profile of mexiletine:

- **Hematology and differential panel:** complete blood count with differential (hematocrit, hemoglobin, mean corpuscular hemoglobin [MCH], mean corpuscular hemoglobin concentration [MCHC], mean corpuscular volume [MCV], platelets, red blood cell count [RBC], white blood cell count [WBC], RBC morphology, basophils, eosinophils, lymphocytes, monocytes, neutrophils)
- **Blood chemistry panel:** ALT (SGPT), AST (SGOT), albumin, calcium, chloride, alkaline phosphatase, bicarbonate, cholesterol, creatine kinase (CK), creatinine, direct bilirubin, Gamma glutamyl transpeptidase (GGT), glucose, phosphorus, potassium, sodium, total bilirubin, total protein, triglycerides, urea nitrogen
- Serum human chorionic gonadotrophin (hCG) for women of childbearing potential (WOCBP) to be completed at screening visit
- Serum or urine human chorionic gonadotrophin (hCG) for women of childbearing potential (WOCBP) to be completed at Baseline (pre-dose), Week 4 and Week 8 visits

All subjects will have safety laboratory tests as above at the Screening Visit and Weeks 4 and 8, or the Final Safety Visit, if applicable. These samples will be analyzed locally at the site's institutional laboratory. If a subject is unable to go to the clinic for the testing, other arrangements may be made with the approval of the NCRI Coordination Center. The Site Investigator may order additional testing, if needed, to further assess an adverse event, or if there is any suspicion that a subject may be pregnant.

7.1.3. Mexiletine Levels/Biomarker Samples

Subjects will have blood drawn to assess a random mexiletine plasma concentration at the Pre-Dose Baseline Visit and Weeks 4, and 8 or the Final Safety Visit, if applicable. Levels will be assayed in a blinded fashion by an experienced clinical pharmacologist at Tufts University

Public Health in Boston, MA. Tufts University will be analyzing plasma for mexiletine trough levels.

Additionally, subjects will have blood drawn for storage and use through the New York Genome Center (NYGC) and the NEALS Biorepository.

7.1.3.1. DNA Collection

Consented patients will have blood drawn for deoxyribonucleic acid (DNA) extraction for genome sequencing at the Baseline Visit. Blood samples will be stored at the New York Genome Center (NYGC) in New York City, NY.

The NYGC will be conducting the sequencing of the de-identified samples, doing the analysis of the sequencing and sharing the results of such sequencing and analysis with researchers pursuant to this protocol, as well as uploading the data to data repositories such as the National Institutes of Health (NIH) Database of Genotypes and Phenotypes (dbGaP).

7.1.3.2. Plasma Collection

Consented patients will have blood drawn for plasma processing, storage and use in the NEALS Biorepository at the Pre-Dose Baseline, Weeks 4, and 8 Visits or the Final Safety Visit, if applicable. These samples will be used for future research in motor neuron diseases.

7.1.4. 12-Lead Electrocardiogram (ECG)

A standard 12-lead ECG will be performed at the Screening Visit, Post-Dose Baseline Visit and Weeks 4, and 8 or the Final Safety Visit, if applicable. A copy of the tracings will be kept on site as part of the source documents. The following measures will be obtained: heart rate, RR interval, PR interval, QRS interval, QT interval, and either Bazett-corrected QT interval or Fridericia-corrected QT interval, and any clinical abnormalities. The ECG will be reviewed same day by the site PI. The following conditions will be brought to the attention of the reviewing cardiologist and medical monitor. The medical monitor will determine if the subject should discontinue study medication.

- any significant change from the screening ECG noted by the reviewing cardiologist
- a PR interval > 200 ms
- a QRS complex > 120 ms
- a QTc interval > 450 ms in males or > 470 ms in females

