13.7. Analysis of Secondary Efficacy Variable

Equivalent models will be used to analyze other pharmacodynamic markers obtained by TMS and NCS and clinical measures of progression. Frequency of muscle cramping will use a similar generalized linear mixed model assuming that weekly counts follow a negative binomial distribution and including participant-specific random slopes with unstructured covariance of random intercepts and slopes. Pain from cramping and interference from fasciculations will be analyzed in similar models assuming a normal distribution and identity link for pain and a multinomial distribution and cumulative logit link for interference from fasciculations.

Analyses of safety will include frequency of AEs compared by negative binomial regression, proportion of participants experiencing a given AE or SAE classified by MedDRA system organ class or preferred term by Fisher's exact test, occurrence of clinically significant clinical laboratory abnormalities by Fisher's exact, and trends in vital signs and ECG parameters by linear mixed models. Participants will be analyzed according to the treatment actually received. With a plan of 40 participants exposed to mexiletine, the study will have an 80% probability of observing at least one instance of any safety outcome expected to occur in at least 4% of exposed patients, or 8% for events unique to a single dose. Comparisons of event rates across doses will be sensitive only to relatively large differences. The study will have 80% power to detect treatment differences in event rates if the rates in the placebo arm are moderately frequent (20% to 50%) and mexiletine exposure increases the odds at least 6-fold.

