3.2.3 Safety Endpoints

The following safety endpoints will be evaluated:

- Proportion of participants experiencing and number of unique events of each type of TEAE and serious TEAE classified by MedDRA system organ class and preferred term,
- Proportion of participants experiencing and number of unique events of TEAEs classified by seriousness, severity, relatedness to study drug, relatedness to TMS and TTNCS procedures, action taken with study drug, action taken with TMS/TTNCS, and outcome, summarized across all MedDRA terms,
- Instances of treatment-emergent and clinically significant laboratory abnormalities classified by assay, whether the abnormality is below or above the normal range,
- Mean change from baseline in weight
- Proportion of participants experiencing treatment-emergent and clinically significant ECG abnormalities by type of finding
- Proportion of participants experiencing treatment-emergent and clinically significant physical examination findings by body system
- Proportion of participants experiencing treatment-emergent neurological examination findings by type of finding

Reported proportions will use as their denominator all participants in the Safety and Tolerability sample (see Section 3.5 below).

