3.8.3 Vital Signs and Weight

The absolute level and the absolute change from baseline for vital signs and weight will be summarized as means, standard deviations, medians, and ranges at each visit by treatment group.

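### QTc may be recorded by either Bazett or Fridericia under a single set of referral limits, and the SAP has no analysis of the ECG intervals that Protocol 13.7 says will be modelled

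*Protocol*

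**What the plan says.** Protocol 7.1.4 schedules a 12-lead ECG at Screening, Post-Dose Baseline, Week 4 and Week 8 (or the Final Safety Visit). The measures include "heart rate, RR interval, PR interval, QRS interval, QT interval", together with "either Bazett-corrected QT interval or Fridericia-corrected QT interval". Neither document says that the choice must be the same for all sites, all patients or all visits of one patient.

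Four conditions send an ECG to the reviewing cardiologist and the medical monitor. Two are limits on PR and QRS. The other two are "a QTc interval > 450 ms in males or > 470 ms in females" and "any significant change from the screening ECG noted by the reviewing cardiologist". On the consequence, the protocol says: "The medical monitor will determine if the subject should discontinue study medication".

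On analysis, Protocol 13.7 plans "trends in vital signs and ECG parameters by linear mixed models". SAP 3.8 has four subsections: adverse events, safety labs, vital signs and weight, and examinations. None is for ECG. The one ECG item in the SAP's list of safety endpoints (3.2.3) is "Proportion of participants experiencing treatment-emergent and clinically significant ECG abnormalities by type of finding". By contrast, SAP 3.8.3 states: "The absolute level and the absolute change from baseline for vital signs and weight will be summarized". The SAP's introduction says that it supplements the protocol and prevails over it where the two differ on analysis.

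**The concern.** There are two linked gaps.

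The first is in measurement. One pair of QTc limits is applied to two quantities that differ whenever the heart rate is not 60 beats/min. Whether a patient is referred can then depend on which formula the site or its machine used. The change-from-screening trigger has the same weakness. Screening is the only ECG before dosing, so a different formula at a later visit would look like a change in QTc with nothing physiological behind it.

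The second is in analysis. The protocol promises to model ECG parameters; the SAP, which governs analysis, contains no summary or model of PR, QRS, QT or QTc. Mexiletine is an antiarrhythmic. The protocol excludes patients with conduction abnormalities or a history of arrhythmia (5.2.2) and bars two other antiarrhythmics because of QT prolongation and arrhythmia risk (6.6.1). Protocol 13.8 bases the choice of dose on safety and tolerability, and 13.7 concedes that comparisons of event rates will pick up only fairly large differences. Interval changes would complement those event counts, and the SAP as written does not produce them.

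**Working it through.** **Formula difference.** The documents state no figure for QTc to reproduce. The limits of 450 and 470 ms come from Protocol 7.1.4. The heart rates and QT values below are assumptions, because the documents give none.

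With RR = 60/HR in seconds:
- Bazett: QTcB = QT / RR^(1/2)
- Fridericia: QTcF = QT / RR^(1/3)
- Hence QTcB / QTcF = RR^(−1/6), which equals 1 only at RR = 1 s, that is, 60 beats/min.

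| Heart rate (beats/min) | QTcB / QTcF | QTcB − QTcF when QTcF = 400 ms | QTcF at which QTcB = 450 ms | QTcF at which QTcB = 470 ms |
|---|---|---|---|---|
| 50 | 0.9701 | −12.0 ms | 463.9 ms | 484.5 ms |
| 60 | 1.0000 | 0.0 ms | 450.0 ms | 470.0 ms |
| 70 | 1.0260 | +10.4 ms | 438.6 ms | 458.1 ms |
| 80 | 1.0491 | +19.6 ms | 428.9 ms | 448.0 ms |
| 90 | 1.0699 | +28.0 ms | 420.6 ms | 439.3 ms |
| 100 | 1.0889 | +35.5 ms | 413.3 ms | 431.6 ms |

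The third column is also the spurious change that a switch of formula between visits would create at unchanged QT and heart rate.

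Single tracings against the male limit of 450 ms:
- 90 beats/min, QT 370 ms: RR = 60/90 = 0.667 s, so QTcB = 370/0.667^(1/2) = 453.2 ms and QTcF = 370/0.667^(1/3) = 423.5 ms. Over the limit by one formula, under it by the other.
- 80 beats/min, QT 390 ms: RR = 0.75 s, giving 450.3 and 429.3 ms. Again on opposite sides.
- 75 beats/min, QT 400 ms: RR = 0.80 s, giving 447.2 and 430.9 ms. Both under the limit, so the choice of formula does not always matter.

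**Can it be undone afterwards?** For analysis, yes. QT and RR are both recorded. In the second example, 450.3 × 0.75^(1/2) / 0.75^(1/3) = 429.3 ms, the same as direct calculation. With one formula throughout, the artefact is 0 ms. A referral already made or missed cannot be corrected this way, and the SAP plans no re-derivation.

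**Protocol against SAP on ECG.** Protocol 13.7 names vital signs and ECG parameters in the same phrase, both to be modelled. SAP 3.8.3 carries the vital signs forward as descriptive summaries. No subsection of 3.8 carries the ECG parameters forward. What remains is the 3.2.3 proportion, for which 3.8 gives no separate analysis.

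**The case against.** A reader might infer that a switch of formula could mimic or hide a drug effect in the comparison of arms. The documents do not support that. Randomisation is stratified by site (Protocol 5.4), and patients, investigators and site staff are blinded (6.5). Nothing ties the choice of formula to treatment, so between arms it adds noise or chance imbalance, not systematic bias. Nor does the SAP plan a QTc estimate that could be distorted.

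Other points stand in whole or part:
- Switching between visits is permitted by silence; the protocol does not say that it will happen.
- Crossing a limit prompts review, not automatic stopping. Each ECG is also read the same day at the site, and the PR and QRS limits do not depend on the formula.
- One should not say that nothing from the ECG list is analysed. Heart rate is among the vital signs summarised under SAP 3.8.3. The 3.2.3 endpoint is a proportion by type of finding and names no judge; only a QTc-type finding could inherit the mixed formula.
- ECG intervals are absent from the safety-variable lists in Protocol 7.1 and 13.1, and Protocol 2.1.3.2 reports no significant ECG changes in the earlier ALS trial, which went up to 900 mg/day.
- Interval means will say little about dose. At Post-Dose Baseline both active arms have had one 150 mg capsule, and Week 8 is off drug. Only Week 4 compares the doses, after a last dose the night before.
- Because the SAP supplements the protocol, its silence might leave the 13.7 model in force. That is arguable, but it leaves two readings where there should be one.

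These points limit the size of the problem. They do not supply a common formula or an ECG analysis.

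**Conclusion.** The point holds as two modest defects. First, the referral rule as written can give different answers for the same tracing. On assumed values the formulas differ by about 10 to 28 ms at 70 to 90 beats/min for a QTcF of 400 ms, by nothing at 60, and with the sign reversed below 60. How often a patient would actually cross a limit on formula alone cannot be worked out from the documents. The effect is on individual referral and on change from screening; between arms it is noise.

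Second, Protocol 13.7 and SAP 3.8 do not match. As the SAP stands, PR, QRS, QT and QTc have no planned summary or model, and the only ECG result it names is the proportion in 3.2.3. This rests on the text alone and needs no assumption.

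Both deserve correction because the remedy is cheap and uses data already collected. Neither touches the primary analysis. No view is taken here on which formula or which limit is right.

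**What to change.** **Protocol 7.1.4:** the sponsor names one correction formula for all sites, patients and visits, and confirms that the stated referral limits are consistent with it.

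**SAP 3.8:** add an ECG subsection that
- derives QTc for every ECG from the recorded QT and RR by that formula;
- summarises level and change from screening in PR, QRS and QTc by arm and visit;
- either applies the linear mixed model of Protocol 13.7 or states that descriptive summaries replace it, so that the two texts agree.

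**Cost:** a protocol clarification and one SAP subsection, with no new measurements. The downside is that some derived QTc values will differ from those printed on the tracing or entered on the CRF, so the SAP should say which value is analysed.

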7.1.5. Physical and Neurological Examinations

A physical examination will be performed and recorded at Screening Visit, Week 4, and Week 8 or the Final Safety Visit, if applicable and will include the following systems: head/neck, eyes, ears, nose/throat, cardiovascular, lungs, abdomen, musculoskeletal, central nervous system, extremities, and skin. In addition, an abbreviated neurological examination will be performed at the Screening Visit, Week 4, Week 8, and the Final Safety Visit, if applicable. The examination will include assessment of mental status, cranial nerves, motor and sensory function, reflexes, coordination, and stance/gait.

7.1.6. Adverse Events

Adverse events will be documented at each study visit, including the Screening Visit once the informed consent form has been signed by the subject. Information on adverse effects of study medication and on inter-current events will be determined at each visit by direct questioning of the subjects, clinical examination, review of concomitant medications, vital signs and laboratory test results. Tolerability will be determined by the ability to complete the study on the assigned treatment at the assigned dose. Subjects on a dose reduction are considered intolerant. Side effects that would not be tolerable in a drug chronically administered are of particular interest. Given the severity of the disease, some significant side effects might be tolerated.

7.2. Outcome Measures

7.2.1. Transcranial Magnetic Stimulation and Threshold Tracking Nerve Conduction Studies

As a *primary outcome measure*, the RMT will be recorded from the abductor pollicis brevis muscle. The RMT is defined as the minimum stimulus intensity required to elicit a 50 μ V MEP in at least 5/10 trials. RMT is thought to reflect the density of corticomotoneuronal projections onto the spinal motor neuron. It is also a biomarker of corticomotor neuronal excitability, in part correlating with persistent sodium current [49].

As *secondary outcome measures*, the slope of the input/output curve of the relationship between stimulus strength and MEP output and the maximum MEP amplitude will also be recorded. The maximum MEP amplitude reflects density of corticomotoneuronal projections onto motor neurons and is affected by cortical hyperexcitability early in ALS and axonal degeneration later in the disease [49]. It is defined as a percentage of the maximum compound muscle action potential (CMAP), to account for lower motor neuron pathology, as measured by standard motor nerve conduction study, which will be performed on the median motor nerve recoding over the APB muscle contralateral to the side of cortical stimulation and just prior to TMS [49]. Maximum MEP amplitudes have been shown to increase in ALS, especially early, reflecting cortical hyperexcitability [49].

Another *secondary outcome measure* to be assessed by TMS, CSP, is recorded as a duration from the onset of the MEP response to resumption of voluntary electromyography activity. The CSP is induced by having patients perform a voluntary contraction, set to 30% of maximal voluntary contraction. The level of contraction will be monitored by recording muscle activity by surface electromyography of the abductor pollicis brevis muscle. The CSP duration is measured from the beginning of MEP to the return of EMG activity. The CSP is thought to be mediated by spinal mechanisms and cortical inhibitory neurons and is a measure of cortical inhibition. Absent or reduced CSP duration is seen in both sporadic and familial ALS patients, most prominently early in the disease [49].

As another key *secondary outcome measure*, changes in SICI, will be measured by dual pulse TMS at the Pre-Dose Baseline Visit, Weeks 4, and 8, and the Final Safety visit, if applicable with conditioned (80% of RMT) and test pulses (120% of RMT) to generate a stable MEP amplitude of 0.2 mV, averaged over interstimulus intervals of 1-7 ms. SICI is thought to reflect refractory cortical axons and subsequent resynchronization of cortico-cortical and corticomotoneuronal

volleys or activation of non-GABAergic cortical inhibitory circuits (initial phase) and synaptic neurotransmission through GABA_A receptors (second phase) [49].

To determine the effects of mexiletine on muscle cramps and fasciculations, 14-day history of fasciculations and a 7 and 30 day history of muscle cramps will be assessed at Baseline and daily summaries of muscle cramping and fasciculations will be completed every morning or evening by participants in a Muscle Cramping/Fasciculations Diary (see Section 7.2.8). Data from the diary will be abstracted by study staff at every visit after the Baseline Visit.

As another *secondary outcome measure* and pharmacodynamic marker, peripheral nerve axonal excitability will be assessed by TTNCS performed at the same visits as TMS using a Digitimer DS5 stimulator. CMAPs will be recorded by standard motor nerve conduction study (NCS) on electromyography machines at each site. Determinations will be made of the strength duration time constant using pulses of varying stimulus duration as this correlates with persistent sodium current [29], have been shown previously to be reduced in patients with muscle cramps using mexiletine [30, 43], and have been shown to predict survival in ALS [29].

There may be up to two TMS physiologists and up to two TTNCS physiologists at each site.

After the screening visits and randomization, ALS subjects will undergo two study visits over the course of 8 weeks with TMS and TTNCS studies at each visit. For these visits, the time of the TMS study (i.e. morning or afternoon) should be kept as consistent as possible. The same TMS and TTNCS physiologist should perform tests at both visits for an individual subject.

As part of the inclusion criteria, a study subject must meet TMS inclusion criteria (resting motor threshold, defined as 50% of pulses eliciting a motor evoked potential (MEP) of amplitude $\geq 50 \mu\text{V}$). A study subject must meet TTNCS inclusion criteria (CMAP $\geq 1.5 \text{ mV}$). Specific attention must be paid to exclusion criteria related to TMS, namely metal in the head and neck region, cardiac pacemaker or brain stimulator, cochlear implants, implanted infusion device or personal history of epilepsy.

All recordings will use the abductor pollicis brevis (APB) muscle on a single hand for the duration of the study. The hand to be recorded will be determined during the neurological exam with the goal of selecting a modestly affected muscle.

- if both sides have MMT score of 5/5, choose the right side
- if both sides are <5 , choose the stronger side
- if one side is 5/5 and the other side is ≥ 3 , choose the weaker side
- if one side is 5/5 and the weak side is <3 , choose the stronger side

TMS Protocol Summary

For TMS recording, motor evoked potentials (MEPs) will be recorded using the Powerlab 26T with LabChart V8 software. The TMS protocol will consist of four components:

- 1) Identification of hot spot and measurement of RMT and maximum MEP amplitude. Both RMT and MEP amplitude must be manually entered into the LabChart software data file.
- 2) Paired testing. This consists of pseudorandomized blocks of:

- Single unconditioned pulses with stimulator output 120% of RMT
- Conditioned pulses (prepulse 80% RMT and test pulse 120% RMT) and interstimulus interval 3 ms for determination of short intracortical inhibition (SICI)
- Single unconditioned pulses with stimulator output 80% of RMT as a control.

3) Input output curves to determine relationship between stimulus strength and MEP output. These are performed over a range from 25% to 100% of maximum stimulus output.

4) Cortical silent period. This will consist of pulses of 120% RMT while subject is activating muscle.

File naming convention and data handling will be specified once all TMS physiologists are confirmed.

TTNCS Protocol Summary

TTNCS will be performed using a Digitimer DS5 stimulator, which is controlled by Qtracs software through a National Instruments Data Acquisition Board. Compound muscle action potentials (CMAPs) will be recorded using the site EMG/NCS machine at almost all sites (requires analog output on EMG machines).

The entire protocol is controlled via the Qtracs software and consists of:

- 1) Setup. It is essential that the physiologist enters his/her unique code, as this is part of the file name. The codes will be assigned once all TTNCS physiologists are confirmed.
- 2) Determination of suprathreshold CMAP amplitude
- 3) Measurement of CMAP response/stimulus relationship
- 4) Determination of strength duration time constant using pulses of varying stimulus duration.
- 5) Recovery cycle analysis. Figure shows threshold change following a single prepulse, illustrating periods of refractoriness, superexcitability and late subexcitability.
- 6) The procedure concludes with recording of final temperature generation of a MEM data file and visual display of the collected data.

File naming convention and data handling will be specified once all TTNCS physiologists are confirmed.

To ensure reproducibility, each neurophysiologist at each site will need to perform TMS and TTNCS on a single unpaid volunteer over three separate days, preferably at the same time of day, and receive approval after review of the data.

